1.0 Objectives

1.1 **Purpose:** We propose a 100-participant randomized controlled 2-arm parallel trial which employs a metagenomic approach to examine how 8 weeks of supervised moderate-intensity treadmill walking exercise (MWE)^{1,2} for 30-45 min 3 times/week alters the gut microbiome, serum SCFAs, and the cardiometabolic profile, body weight, and body composition of individuals 30-64 years old who are overweight or obese and have PreD.

Aim 1: Compare the effect of 8 weeks of MWE vs. control on shifts in the gut microbiome of overweight or obese individuals with PreD. **H1:** Gut microbial diversity and functional capacity (specifically, genes relevant to SCFA production) will increase improve after 8 weeks in the experimental group vs. control.

Aim 2: Compare the effect of 8 weeks of MWE vs. control on changes in serum SCFAs. **H2:** Serum Levels of SCFAs butyrate, acetate, and propionate will increase after 8 weeks in the experimental group vs. control.

Aim 3: Use formal mediation methods to estimate the proportion of MWE-induced changes in participants' cardiometabolic profiles, body weight, and body composition that are mediated by changes in the gut microbiome and/or serum SCFAs. **H3:** MWE-induced changes in the gut microbiome and serum SCFAs will partly explain changes in participants' cardiometabolic profile (e.g., blood lipids, fasting insulin/glucose, blood pressure, waist circumference), body weight, and body composition.

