3.0 Study Endpoints/Events/Outcomes

3.1 **Primary Endpoint/Event/Outcome:** Expanded data collection procedures for our primary and secondary outcomes are available in Section 5.2. We have two Primary Outcomes. The first primary outcome is changes to the gut microbiome, assessed via metagenomic sequencing, from pre- to post-intervention (**Specific Aim 1**). The Shannon Index—a measure of microbial community diversity with good reproducibility (ICCs>0.50)⁵⁶—will be our primary indicator for changes in gut microbiota composition, and will be assessed at baseline, and following the 4th and 8th weeks. The second primary outcome is serum SCFA levels. Participants will undergo fasted blood draws to assess serum SCFA levels (**Specific Aim 2**). This work will be performed using the Metabolon pipeline.⁵⁷

3.2 **Secondary Endpoint(s)/Event(s)/Outcome(s):** We have several Secondary Outcomes. For **Specific Aim 3** cardiometabolic profiles will be assessed via assays for high-density lipoprotein cholesterol (HDL-C), triglycerides, fasting insulin/glucose, and c-reactive protein (CRP). All blood assays will be conducted by the *UMN Advanced Research and Diagnostic Laboratory* (see ‘Facilities’ document). Blood samples collected will be stored at -80°C prior to batch-processing. Resting blood pressure (BP) will be taken using an Omron Automatic BP Cuff (Omron; Lake Forest, IL), with the average of the last two BP measurements reported. These cardiometabolic indices form the foundation of the ‘metabolic syndrome’,⁵⁹⁻⁶³ and we will form a composite continuous score for cardiometabolic disease risk from HDL-C, fasting glucose, triglycerides, the average of systolic and diastolic BP, and waist circumference. Specifically, z-scores for each biomarker will be calculated and the within-participant average across z-scores computed and referred to as *cardiometabolic disease risk (CMDrisk*; the primary dependent variable for Specific Aim 3). This score has been used in epidemiologic, experimental, and clinical studies.^{62,64-67} Individual components will be described in secondary analyses as needed. We will also measure HbA1c using whole blood analyzed at the UMN Advanced Research Diagnostic Laboratory; the A1cNOW+® device may also be used in a limited capacity to assess validity.⁶⁸ The oral microbiome will be

MEDICAL PROTOCOL (HRP-590)

PROTOCOL TITLE: Exercise and the Gut Microbiome R21

VERSION DATE: 05/11/2022

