15.0 Statistical Considerations

15.1 Data Analysis Plan: Chi-square and independent *t*-tests will evaluate baseline group differences as appropriate. Mediation analyses will also be conducted. We outline our analysis plans in Section 15.3. ⁸⁶⁻⁹²

MEDICAL PROTOCOL (HRP-590)

PROTOCOL TITLE: Exercise and the Gut Microbiome R21

VERSION DATE: 05/11/2022

15.2 Power Analysis: Power for Aim 1 is based on analyses using alpha-diversity (Shannon Index) as the primary outcome. Taniguchi et al.⁴⁶, reported a mean \pm SD baseline Shannon Index of 5.7 ± 0.6 which is consistent with preliminary data from gut samples collected by [name] in other recent projects. Given this variance, and with a balanced design of $n=50$ in the experimental and control arms ($N=100$ total), we will have >99% power to detect a 1 unit increase in Shannon Index. Power for Aim 2 is based on changes in serum SCFAs. Our SCFA assays will be performed at Metabolon and our colleagues at Metabolon provided information on mean \pm SD for these outcomes in their lab. They are as follows: acetate= 1806 ± 2500 ng/mL, butyrate= 35 ± 43 ng/mL, and propionate= 50 ± 52 ng/mL. With these distributions, we will have >80% power to detect a difference in SCFA levels between treatment and control groups with a magnitude of at least 50% of 1 SD.

The primary outcome for Aim 3 will be a composite score based on the average of the z-scores for the following 5 biomarkers: HDL-C, fasting glucose, triglycerides, average of systolic and diastolic BP, and waist circumference. The standardized mean \pm SD of this *CMDrisk* z-score in [name] sedentary behavior intervention among 575 participants (Grant #: R01CA198971) is 0 ± 0.7 . This provides 80% power to detect a difference in the *CMDrisk* z-score of 0.4, between intervention and control at the conclusion of the study.

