15.3 Statistical Analysis: Aim 1 analysis: Gut microbiome data, derived via metagenomic sequencing, will be operationalized as described above. In a primary analysis, generalized linear regression models will regress Shannon Index on intervention assignment. The model is formalized as: $E[Y] = \text{intercept} + \beta_1 * A + \beta_2 * C$. $E[Y]$ =expected Shannon value; β_1 =coefficient for intervention arm; β_2 =coefficient for a vector of confounders should this be necessary in our randomized design. Secondary analyses will consider metagenomic features (genes and functional profiles). Any metagenomic features not present at >0.1% relative abundance in at least 10% of samples will be removed. Zero-inflated log-linear generalized linear models with a Gaussian error term will be fitted, with treatment status as predictor, as implemented by the metagenomeSeq Bioconductor package for shotgun metagenomic data analyses.⁹³ The generalized model, per metagenomic outcome, is formalized as: $\log E[Y] = \text{intercept} + \beta_1 * A + \beta_2 * C$. $E[Y]$ =expected normalized sequence count value; β_1 =coefficient for intervention arm; β_2 =coefficient corresponding to the vector of baseline confounders. Total read count is incorporated as an offset term. This analysis will generate a “top list” of genes, gene families, and pathways with altered abundance by intervention assignment. Separate models will

MEDICAL PROTOCOL (HRP-590)

PROTOCOL TITLE: Exercise and the Gut Microbiome R21

VERSION DATE: 05/11/2022

be developed for intervention status predicting week 4 and week 8 outcomes. We will also consider time*treatment status models to incorporate stool sampling at all three timepoints. P-values will be corrected for multiple hypothesis testing using the false-discovery rate as we have done previously with high dimensional data.^{86-92,94-98}

Aim 2 analysis: As with Aim 1, generalized linear regression models will be used. Each of three SCFAs (acetate, butyrate and propionate) will be regressed on intervention assignment. The model is formalized as: $E[Y] = \text{intercept} + \beta_1 * A + \beta_2 * C$. $E[Y]$ =expected SCFA value; β_1 =coefficient for intervention arm; β_2 =coefficient for a vector of confounders.

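### The primary Shannon and SCFA models in Section 15.3 are not committed to adjusting for the outcome's own baseline value, although that value is measured before randomisation

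*Combined protocol and SAP*

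**What the plan says.** **Models (Section 15.3).** For Aim 1, "generalized linear regression models will regress Shannon Index on intervention assignment". The formula has an intercept, an arm term and a vector C, whose coefficient is described as the "coefficient for a vector of confounders should this be necessary in our randomized design". For Aim 2 the three SCFAs follow the same pattern: "acetate, butyrate and propionate) will be regressed on intervention assignment", again with a vector of confounders. C is not listed for either aim. Only the secondary metagenomic-feature model refers to baseline covariates ("coefficient corresponding to the vector of baseline confounders"), and it does not list them. For stool, the plan adds: "We will also consider time*treatment status models to incorporate stool sampling at all three timepoints".

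**Scale of the outcome.** Section 15.3 models an expected Shannon or SCFA value and speaks of week 4 and week 8 outcomes. Other sections speak of change:
- Section 1.1, Aim 2: "Compare the effect of 8 weeks of MWE vs. control on changes in serum SCFAs".
- Section 3.1, repeated in 5.2, first primary outcome: "changes to the gut microbiome, assessed via metagenomic sequencing, from pre- to post-intervention".
- Section 15.2: "Power for Aim 2 is based on changes in serum SCFAs". The same paragraph then describes a difference in SCFA levels.

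**Availability of baseline.** Under Section 5.2 the stool sample and the fasting blood draw belong to run-in week 3, and randomisation follows once all measures are complete.

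**The concern.** Each primary outcome is measured in every participant before randomisation, and an earlier value of the same quantity is usually the strongest predictor of the later one. A plan that leaves it out, or leaves it to later judgement, gives up precision that costs nothing to obtain. It also leaves the primary model open: two analysts could follow Section 15.3, put different things into C, and report different primary estimates. Section 15.1 plans baseline group tests, and nothing rules out using them to decide which covariates are needed.

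The SCFA outcome has most at stake. It is planned at half an SD, and fasting blood is drawn only at baseline and week 8, so baseline is the only repeat SCFA measure available.

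**Working it through.** **Inputs from the documents.** 50 per arm (Sections 10.1 and 15.2); 20% attrition (10.1); Shannon SD 0.6 and target 1 unit; SCFA target 0.5 SD with more than 80% power; SCFA mean ± SD of 1806 ± 2500, 35 ± 43 and 50 ± 52 ng/mL for acetate, butyrate and propionate (15.2).

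**Assumed.** Alpha 0.05 per test, since neither alpha nor sidedness is stated for these comparisons. r = 0.3, 0.5, 0.7. The reproducibility figure in Section 3.1 (ICCs above 0.50) is loose support for Shannon only; nothing in the documents bears on r for SCFAs.

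**The plan's own figures.** The standard error of a difference is SD × √(2/n) = 0.2 SD at n = 50.
- Aim 1: 1/(0.6 × 0.2) = 8.33 standard errors, so power is above 99.99%. The stated figure of more than 99% reproduces.
- Aim 2: 0.5/0.2 = 2.5 standard errors. By noncentral t, power is 69.7% two-sided and 79.9% one-sided (70.5% and 80.4% by normal approximation). The stated figure of more than 80% is matched only approximately, and only if the test is one-sided.

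**Residual variance**, with s² the week 8 variance:
- unadjusted level: s²
- adjusted for baseline (ANCOVA): s²(1 − r²), a saving of r²

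This gives 0.3² = 9%, 0.5² = 25% and 0.7² = 49%.

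**SCFA power at 0.5 SD** (noncentral t, one degree of freedom charged to ANCOVA):

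| Setting | Level | ANCOVA r = 0.3 | r = 0.5 | r = 0.7 |
|---|---|---|---|---|
| 50 per arm, two-sided | 69.7% | 73.7% | 81.5% | 93.4% |
| 50 per arm, one-sided | 79.9% | 83.1% | 88.9% | 96.7% |
| 40 per arm (100 × 0.8 / 2), two-sided | 59.8% | 63.9% | 72.2% | 87.1% |

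Two-sided ANCOVA reaches 80% at r of about 0.47 with 50 per arm and about 0.62 with 40. At low r it helps but does not reach 80%.

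**Shannon difference detectable with 80% power** (SD 0.6, 50 per arm, two-sided): level 0.34; ANCOVA 0.32, 0.29, 0.24.

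**If the outcome were a change score.** With k the ratio of baseline SD to week 8 SD, the change has variance s²(1 + k² − 2rk), and ANCOVA saves 1 − (1 − r²)/(1 + k² − 2rk). With equal SDs (k = 1) this is (1 − r)/2 = 35%, 25%, 15%. At k = 0.8, chosen for illustration, it is 22%, 11%, 2%; at k = 1.25 it is 50%, 43%, 37%. The saving is never negative, but its size depends on k, which the documents do not give.

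**Skewness.** Each SCFA SD exceeds its mean (2500/1806 = 1.38, 43/35 = 1.23, 52/50 = 1.04) for a quantity that cannot be negative, so raw values cannot be near normal. The power figures apply on whatever scale makes the data near normal. If values were lognormal (an assumption), a log-scale r of 0.5 would be only about 0.37 to 0.41 on the raw scale.

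**The case against.** **C could already hold the baseline value.** It could, and the plan does not forbid it. But Section 15.3 names age, sex, race/ethnicity and PA duration where it fixes covariates for Aim 3, and names nothing for Aims 1 and 2. This stands as a reason to call it a missing commitment, not a wrong model.

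**A reader might infer that the plan is evenly split between a level and a change score.** The documents do not support that. Section 15.3 models values and week 4 and week 8 outcomes, and the Aim 3 text says 8-week change when it means change. The operative text leans to a level. The wording in Sections 1.1, 3.1, 5.2 and 15.2 is an inconsistency to align, and the change-score comparison is secondary.

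**A reader might infer bias.** There is none from this source: under randomisation the level, the change score and ANCOVA all estimate the same effect.

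**A reader might infer that the baseline tests in Section 15.1 will select the covariates.** The plan does not say so; it only leaves the possibility open.

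**The gains depend on assumptions.** This stands. r is assumed, one-sided testing shrinks the gain at 50 per arm from about 4 to 24 points to about 3 to 17, skewness may lower r on the raw scale, and no correction for three SCFAs is applied. None of this reverses the direction.

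**The three-visit model may supply the adjustment.** It is only to be considered and covers stool only. With categorical time, complete data and no constraint on baseline means, its week 8 contrasts reproduce the change or the level comparison. With dropout that equivalence is no longer exact, but baseline handling is still unstated.

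**Conclusion.** The point holds as one of precision and pre-specification and should be corrected. Section 15.3 does not commit either primary model to the outcome's own baseline value. Against the unadjusted week 8 level that the text leans to, the commitment removes r² of the residual variance. For SCFAs at 0.5 SD and 50 per arm, two-sided, that is worth about 4, 12 and 24 points of power at r = 0.3, 0.5 and 0.7, on normal-theory figures with r and alpha assumed. For Shannon it matters only for differences well below the stated 1 unit. Apart from one degree of freedom, ANCOVA is at least as precise as a level or a change score at any r, so the choice can be made without knowing r. A reader might go further and conclude that adjustment rescues the Aim 2 power claim. That is not established: it depends on r, sidedness and retention, and at 40 per arm two-sided power is still 72% at r = 0.5.

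**What to change.** In Section 15.3:
- Define Y in each primary model as the week 8 value.
- Enter the baseline value of the same outcome (Shannon, or the same SCFA) as a fixed covariate, on the same scale as Y; for example, log-transform both if a log scale is used for SCFAs.
- State that this covariate is included whatever the Section 15.1 baseline tests show, and remove the conditional clause for it in Aim 1.
- If the three-visit Shannon model is used, adjust for baseline or constrain baseline means to be equal across arms.

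In Sections 1.1, 3.1, 5.2 and 15.2, state that the effect is the baseline-adjusted difference at week 8.

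The cost is wording in those five sections, one degree of freedom per model, and a short rule for a participant whose baseline assay is missing. No new data or visits are needed.

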9.2 Additional Safeguards: N/A**10.0 Local Number of Participants**

10.1 Local Number of Participants to be Consented: We will recruit participants on a rolling basis with the help of our clinical partners within community-based health clinics and community outreach around Minneapolis-St. Paul. We will assume a 20% attrition rate based on documented attrition rates of PA interventions,⁸²⁻⁸⁴ along with a 30% rate of individuals who fail to fall within the HbA1c eligibility range during screening. With these rates in mind, we will recruit 150 individuals total to meet our desired overall N of 100 participants (n = 50 per group). Given the need for participants to be

MEDICAL PROTOCOL (HRP-590)

PROTOCOL TITLE: Exercise and the Gut Microbiome R21

VERSION DATE: 05/11/2022

able to participant in the exercise intervention at the Epidemiology Clinical Research Center, all participants will be recruited locally.

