12.0 Withdrawal of Participants

12.1 Withdrawal Circumstances: We do not foresee any circumstances under which participants will be withdrawn from the research without their consent. Participants who discontinue from the active intervention due to illness or injury will still be invited to complete all study measures at all data collection time points.

12.2 Withdrawal Procedures: For participants who ask to withdraw from the study voluntarily, no additional data will be collected and participants would be compensated at the prorated rate as described in Section 11.4. would still be compensated according to the table above. However, data from the participant's time in the study will still be used in data analysis when employing an intent-to-treat analysis approach.

12.3 Termination Procedures: We do not foresee any circumstances that would result in the termination of the study for any individual.

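### The primary Shannon regression uses one value per participant and states no missing-data method, which fits poorly with the intent-to-treat statement at 20% expected attrition; the model using all three stool samples is only optional

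*Combined protocol and SAP*

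**What the plan says.** Section 15.3 (Aim 1) gives the primary analysis: "generalized linear regression models will regress Shannon Index on intervention assignment". The formula is E[Y] = intercept + β1·A + β2·C, where A is arm and C is a vector of confounders to be used if needed. Y is a Shannon value, and the formula names no visit. The paragraph then turns to secondary analyses of metagenomic features. After that come a sentence on separate week-4 and week-8 models and this one: "We will also consider time*treatment status models to incorporate stool sampling at all three timepoints".

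Section 12.2 says: "For participants who ask to withdraw from the study voluntarily, no additional data will be collected". It adds that "data from the participant's time in the study will still be used in data analysis when employing an intent-to-treat analysis approach". Section 12.1 says that those who stop the intervention through illness or injury "will still be invited to complete all study measures at all data collection time points".

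Section 10.1 says: "We will assume a 20% attrition rate based on documented attrition rates of PA interventions". Section 3.1 schedules Shannon at baseline, week 4 and week 8, and describes it as "a measure of microbial community diversity with good reproducibility (ICCs>0.50"). Section 15 does not mention intent-to-treat, an analysis set, missing data or imputation.

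**The concern.** Stool is collected three times, but the stated primary model takes one value per person. Someone who withdraws after week 4 leaves two usable samples, and neither enters a week-8 regression on arm. The statement in Section 12.2 therefore has no counterpart in the analysis section for the contrast that matters most.

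Two things are at stake. One is precision: the model names no baseline value, although every randomised participant should have one. The other is bias. Only one arm exercises, so dropout could plausibly differ between arms. If it does, and if it is related to Shannon, a week-8 comparison of those who remain can be shifted even when exercise has no effect. A model that also uses baseline and week 4 corrects for the part of dropout that those observed values explain.

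**Working it through.** **Inputs.** Shannon SD 0.6 and 50 per arm (Section 15.2); 20% attrition (Section 10.1), giving 50 × 0.8 = 40 per arm with a week-8 value. Assumed, because the documents do not give them: two-sided alpha 0.05; equal loss in the two arms for the precision figures; between-visit correlation ρ = 0.5, at the edge of the ICC figure in Section 3.1, with 0.3 and 0.7 as a range.

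**The plan's own figure.** SE = 0.6 × √(2/50) = 0.120, and 1/0.120 = 8.33, so power for a 1-unit difference exceeds 99.99%. The stated >99% reproduces. At 40 per arm, SE = 0.6 × √(2/40) = 0.134 and power still exceeds 99.9%. The 80%-power difference is (1.960 + 0.842) × SE: 0.336 at 50 per arm and 0.376 at 40. Power for a 0.3-unit difference falls from 70.5% to 60.9%.

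**Precision at 40 completers per arm.**
- Unadjusted week-8 regression: SE = 0.134.
- Week-8 regression with baseline Shannon as covariate: 0.134 × √(1 − ρ²) = 0.134 × 0.866 = 0.116.
- Three-timepoint model with common baseline mean, by generalised least squares with equal correlations, 10% lost before week 4 and 10% after: 0.115.

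| ρ | Unadjusted | Baseline-adjusted | Three timepoints |
|---|---|---|---|
| 0.3 | 0.134 | 0.128 | 0.128 |
| 0.5 | 0.134 | 0.116 | 0.115 |
| 0.7 | 0.134 | 0.096 | 0.095 |

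At ρ = 0.5 the 80%-power difference goes from 0.376 to 0.326 with baseline and 0.324 with all three timepoints. With unrounded SEs (0.1342, 0.1162, 0.1155), the share of the variance gain due to baseline alone is (0.1342² − 0.1162²)/(0.1342² − 0.1155²) ≈ 96%.

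**Bias, worst case, true effect zero.** Suppose one arm loses, after week 4, the 20% with the lowest week-4 values, and loss in the other arm is random. The shift in the week-8 completer contrast is ρ × 0.6 × φ(0.8416)/0.8 = 0.5 × 0.6 × 0.280/0.8 = 0.105. That is 0.105/0.134 = 0.78 SE. The type I error is then P(Z > 1.96 − 0.78) + P(Z < −1.96 − 0.78) ≈ 12%. At ρ = 0.7 the bias is 0.147.
- Baseline adjustment alone leaves 0.105 × (1 − 0.5) ≈ 0.053.
- Using baseline and week 4 leaves about zero, provided all the loss follows week 4. If half of this selected loss occurs before the week-4 sample, about 0.024 remains.

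**Bias, milder case.** A simulation (4,000 runs, about 22% lost overall) let exercise-arm dropout become more likely as week-4 Shannon fell and made control dropout random. The completer contrast was off by 0.064 at ρ = 0.5 and 0.085 at ρ = 0.7. With baseline as covariate, 0.033 and 0.027 remained; with baseline and week 4, 0.002 and 0.000. When dropout was completely random, every estimator was within 0.003 of zero.

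**The case against.** A reader might infer that the intent-to-treat statement cannot be met, or that the plan discards everyone without a week-8 sample. The documents do not go that far. Section 15.3 states no complete-case rule; the exclusion is what the written model does when no missing-data method is given. A participant who leaves after week 4 could enter a week-4 model. Under Section 12.1, people who stop exercising through illness or injury are still invited to every visit, so the loss concerns voluntary withdrawals and missed samples.

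A reader might also infer that the deciding contrast is left open. That is mostly answered elsewhere: Section 1.1 speaks of effects after 8 weeks and Section 3.1 of pre-to-post change. Section 15.3 simply does not repeat it. The sentences on separate-visit and three-timepoint models follow the text on metagenomic features and may describe only those. They should not be attached to Shannon without that caution.

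The figures also invite over-reading. The variance ratio of 1.35 between the unadjusted and three-timepoint models (0.1342²/0.1155²) is not the benefit of a longitudinal model, because baseline adjustment supplies nearly all of it, and C could hold the baseline value although it is not named. The 12% type I error is a constructed extreme; the documents give no arm-specific dropout rates. Nor does a completer analysis need dropout to be unrelated to earlier values: if dropout works the same way in both arms, there is little or no bias under the null. These objections limit the size of the point. They do not supply the missing analysis set or missing-data method.

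**Conclusion.** The point holds as a gap in the primary analysis that is worth closing. The Shannon model as written takes one value per participant, names no baseline value and does not say how missing week-8 samples are handled. At the planned attrition about 20 of 100 randomised participants could be absent from the week-8 contrast.

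Under the assumptions above, the precision available is a fall in SE from 0.134 to about 0.115–0.116 at correlation 0.5, almost all of it from baseline. The particular value of week 4 is protection against dropout that differs by arm and depends on observed values. How large that bias would be in this trial cannot be known from the documents; 0.105 is a worst case. The planned 1-unit effect is not in danger. The consequence is for smaller effects and for having the analysis fixed in advance.

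**What to change.** In Section 15.3, make the primary Aim 1 analysis a repeated-measures model of Shannon at baseline, week 4 and week 8, in all randomised participants with at least one sample. Include arm by time, a common baseline mean and an unstructured covariance. Name the week-8 arm difference as the single primary contrast and week 4 as secondary. A baseline-adjusted week-8 regression with multiple imputation using baseline and week 4 is an acceptable equivalent.

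Define the intent-to-treat set in Section 15 so that it matches Section 12.2, and say whether the separate-visit and three-timepoint sentences cover Shannon, the metagenomic features or both.

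For the SCFAs, Section 5.2 has no week-4 blood draw, so adjust for the baseline value; little can be recovered from withdrawers.

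The cost is SAP wording and slightly more programming. No new data or visits are needed.

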During weeks 7 and 8, participants will complete 3 unannounced phone-based dietary recalls. During week 8, participants will again consume their 3-day standardized meal plan, obtain a fecal sample, and complete a study assessment visit (same measures as described above in run-in week 3).

Table 1. Timing of Data Collection events during the 3-Week Run-In and Intervention Weeks 4 & 7/8.

Day 1	Day 2	Day 3	Day 4	Day 5	Day 6	Day 7
				Stool (pm)*	Stool (am)*	Stool
		Standard Diet Day1	Standard Diet Day2	Standard Diet Day3		
						Assess. Visit

**Preferred timing stool collection is the evening of Day 5 or morning of Day 6, though anytime in the Day 5 – 7 window is acceptable.*

Group 2 (Control group): Participants will be asked to maintain their usual PA during the initial 8-week intervention period but will undergo all data collection procedures as outlined above for the experimental group.

Expanded Data Collection Procedures: We have two **Primary Outcomes**.

The first primary outcome is changes to the gut microbiome, assessed via metagenomic sequencing, from pre- to post-intervention (**Specific Aim 1**). The Shannon Index will be our primary indicator for changes in gut microbiota composition. Participants will use the OMNIgene-Gut stool collection kit to obtain their fecal samples collected at baseline, week 4 and

MEDICAL PROTOCOL (HRP-590)

PROTOCOL TITLE: Exercise and the Gut Microbiome R21

VERSION DATE: 05/11/2022

week 8. The home-collected samples will be returned to our lab within 30 days. DNA will be extracted from the stool samples using the 96 well plate Mo Bio Power soil kit on an Epmotion robot and eluted into 50ul aliquots. Each extraction will contain negative and positive controls representing defined bacterial communities (Zymo; Irvine, CA). DNA will be quantified using Quant-it and stored at -80°C. Metagenomic libraries will be prepared at the *UMN Genome Center* (see 'Facilities' document) using the Nextera XT kit (Illumina; San Diego, CA) and barcoded. DNA libraries will be denatured with NaOH and diluted to 8-12 pM in Illumina's HT1 buffer, spiked with 1% PhiX and a HiSeq 1x100 cycle v3 kit Illumina HiSeq, with an expected output of at least 0.5 million total sequences per sample. This approach has been shown to be valid⁵⁴ and represents an approach that can address both gut microbial taxonomy and community functional content at a cost similar to 16S studies.

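### The single 0.1% abundance filter in section 15.3 would remove most single genes if the gene catalogue is large, and may remove the SCFA-production genes on which the functional half of H1 rests

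*Combined protocol and SAP*

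**What the plan says.** H1 in section 1.1 has two halves, diversity and function. The functional half predicts that "functional capacity (specifically, genes relevant to SCFA production) will increase" in the exercise arm relative to control. It names a class of genes and no individual gene.

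The functional data are handled in section 15.3, under Aim 1: "Secondary analyses will consider metagenomic features (genes and functional profiles"). The next sentence is the filter: "Any metagenomic features not present at >0.1% relative abundance in at least 10% of samples will be removed". One model per surviving feature then yields a top list of "genes, gene families, and pathways with altered abundance by intervention assignment", with false-discovery-rate correction.

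Section 15.3 does not give:
- a separate threshold for any feature level;
- the denominator of relative abundance;
- whether the 10% is counted within a visit or over all visits;
- a list of SCFA genes, or an exemption for them.

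On depth, section 5.2 describes shallow shotgun sequencing "with an expected output of at least 0.5 million total sequences per sample".

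**The concern.** A relative-abundance cut-off acts very differently on a list of a hundred items and on a list of many thousands. Shares sum to 100%, so the longer the list, the smaller the typical share. A rule that leaves a pathway table largely intact can empty a gene table.

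The SCFA genes have no other route to a test. The primary Aim 1 model concerns the Shannon Index, Aim 2 concerns serum SCFAs, and the Aim 3 mediators are β-diversity and serum SCFAs. If the filter removes the SCFA genes, they will be missing from the top list for a reason unrelated to exercise. A reader of the results would have no means of telling that from a true null. Section 2.1 presents the assessment of functional capacity as part of what is new in this trial, so the loss would matter even though the analysis is secondary.

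**Working it through.** **The plan's own figure.** The only power statement for Aim 1 (section 15.2) is more than 99% for a 1-unit Shannon difference, SD 0.6, 50 per arm. Assuming two-sided alpha 0.05, since none is stated, I get more than 99.99%, so the figure reproduces. It covers the diversity half of H1 only. The plan gives no figure for the functional half or for the number of features that survive the filter.

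**Inputs from the documents.** Cut-off above 0.1% in at least 10% of samples (15.3); at least 500,000 sequences per sample (5.2); 100 participants, 50 per arm (10.1); three stool samples each (3.1), so up to 300 samples.

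**Step 1: reads needed.** 500,000 × 0.001 = 500 reads. If every read is assigned, a feature at 0.02% has 100 reads and one at 0.01% has 50. The Poisson coefficient of variation is 1/√reads: 4.5% at 500, 10% at 100, 14% at 50. The rule therefore discards features for which counting error is modest.

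**Step 2: how many features can pass.** Shares sum to 1, so at most 999 features can exceed 0.1% in one sample. Over samples the ceiling is higher, because different samples may pass different features. With 100 samples at one visit, 10 must pass: 999 × 100 / 10 = 9,990. With 300 samples, 30 must pass: 999 × 300 / 30 = 9,990. That ceiling is reached only if samples share almost no features.

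**Step 3: share of one gene (assumed lengths).** Take genes of 0.5 to 1.5 kb, genomes of 2 to 6 Mb, one copy per genome and all reads as denominator. Share = gene length / genome length.
- Carried by every cell: 0.5/6,000 = 0.008% to 1.5/2,000 = 0.075%.
- Carried by 20% of cells: 0.002% to 0.015%.

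All are below 0.1%.

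**Step 4: gene counted within one species (assumed gene number).** Ceiling = species share / genes per genome, for genes of equal length. With 1,000 to 5,000 genes this is 0.1% to 0.02% if the species is the whole community, and 0.02% to 0.004% at a 20% share. None exceeds the cut-off.

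**Step 5: simulation of the rule.** 100 samples, log-normal abundances, between-feature log-SD 1 to 2.5, between-sample log-SD 0.7, one run per setting. These values and the list sizes are assumptions. The range is over the four between-feature log-SDs tried (1, 1.5, 2, 2.5).

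| Features in the list | Share kept |
|---|---|
| 200,000 | 0 to 0.1% |
| 50,000 | 0 to 0.6% |
| 10,000 | 1.7 to 3.4% |
| 5,000 | 5.7 to 9.0% |
| 2,000 | 13 to 30% |
| 500 | 8 to 82% |
| 300 | 35 to 86% |
| 100 | 58 to 100% |

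Near-total loss is thus a feature of large single-gene catalogues. At 2,000 to 10,000 features, a plausible size for gene families pooled over species (assumed), some hundreds remain (165 to 598). Lists of pathway size keep roughly a third or more.

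**The case against.** A reader might infer that the functional half of H1 cannot be tested at all, or that the SCFA genes are certain to be discarded. The documents do not support either.

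- Section 15.3 also analyses gene families and pathways, and H1 speaks of a class of genes under the head of functional capacity. Features that survive at those levels bear on H1. This stands, and it rules out the stronger reading. It does not remove the problem: the simulation shows that some features survive, not that SCFA features are among them. The every-cell case in step 3 already pools over species and still stops at 0.075%.
- The shares in step 3 depend on the chosen ranges. If half the reads are assigned and the denominator is assigned reads, 0.075% becomes 0.075/0.5 = 0.15%, which passes. A 2.5 kb gene in a 2 Mb genome is 2.5/2,000 = 0.125%, which also passes. Pooling several copies into one feature raises the share further. This stands. For a gene carried by 20% of cells, however, even the upper value of 0.015% would pass only if fewer than 15% of reads were assigned. The model's total-read offset hints at an all-reads denominator but does not settle it.
- The limit of 999 is per sample and does not show that SCFA genes fall outside the set that passes. Correct.
- Poisson error is not the whole error. Variation between people adds to it, so a low count floor has a price. Correct, and it bears on the fix.
- These are secondary analyses. The Shannon model has no such stated filter, and serum SCFAs are untouched. Correct, and it limits the reach of the point.

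**Conclusion.** The concern holds at gene level. A stated rule, applied before the only planned functional test, demands 500 reads per feature at the planned minimum depth and lets at most 999 features through per sample. With a catalogue of tens of thousands of genes or more, it would remove nearly all single genes: at most 0.6% were kept at 50,000 or more under the simulated assumptions. It may remove the SCFA-production genes, and nothing in the plan protects them.

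The number of SCFA features lost cannot be derived. It depends on the denominator, the catalogue size, pooling over species and the abundances of these genes, none of which is given. Gene families and pathways may partly survive. The primary Aim 1 and Aim 2 analyses are not affected. The plan should be changed before functional results are examined by arm.

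**What to change.** 1. Define the denominator of relative abundance (all reads, mapped reads or reads assigned at that feature level), and say whether the 10% is counted per visit or over all samples.
2. For genes and gene families, replace the flat 0.1% cut-off with a lower count-and-prevalence filter, set without knowledge of arm. Cut-offs 10 to 100 times lower correspond to about 50 to 5 reads at 500,000 sequences, with Poisson CV 14% to 45% (1/√50 to 1/√5), so the floor should be justified within that trade-off. Section 15.3 applies its filter to functional features and states no rule for taxa, so nothing there needs preserving on that account.
3. List the SCFA-production genes or pathways in advance and exempt them from the abundance filter. Compare them between arms at week 8 adjusting for baseline, either one by one with false-discovery-rate correction within that list, or as a single length-normalised summed score. Name which of the two is used.
4. Keep the corrected top list of all other features as exploratory.

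The cost is plan text and one added analysis, with no new samples, visits or participants. The downside is a longer exploratory list to correct over, with some sparse features in it.
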